### 3.3 Primary endpoints

The primary endpoints for the three primary objectives are:

1. Composite MACE at 30 days post vaccination (preferred by cardiovascular community) and at 42 days post vaccination (preferred by vaccine monitoring investigators) including any of:
  - Death from any cause.
  - Ventricular arrhythmia (ventricular fibrillation or ventricular tachycardia).
  - Heart block (type II or type III block).
  - Heart failure (national guideline criteria).
  - Left ventricular systolic dysfunction (left ventricular ejection fraction [LVEF] <55%).
  - Cardiac tamponade.
2. Recovery of cardiac function in patients with previously documented abnormal cardiac function (LVEF<55% during anytime at baseline), with LVEF increase by 5% from worst baseline measurement.
3. Quality of life, depression, anxiety, and physical activity using validated instruments at baseline, 3 months, 12 months, and annually.
  - 3a. Quality of life: EQ-5D-5L questionnaire for adults or EQ-5D-Y questionnaire for children.
  - 3b. Depression and anxiety data: PHQ-9 and GAD-7.
  - 3c. Physical activity: International Activity Questionnaire.

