## 3. STUDY OBJECTIVES AND OUTCOMES

### 3.1 Primary objectives

1. Evaluate the incidence, type, and severity of major adverse cardiovascular events (MACE) in patients with vaccine associated myocarditis/pericarditis, COVID-19 myocarditis/pericarditis, and MIS-C/A myocarditis.

2. Assess cardiac function recovery in patients with vaccine associated myocarditis/pericarditis, COVID-19 myocarditis/pericarditis, and MIS-C/A myocarditis.
3. Evaluate functional outcomes including quality of life, depression, anxiety, and physical activity in patients with vaccine associated myocarditis/pericarditis, COVID-19 myocarditis/pericarditis, and MIS-C/A myocarditis.

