### 3.4 Secondary endpoints

- Individual components of primary composite endpoint at 30 days and 42 days post vaccination.
- Atrial arrhythmias.
- All-cause and cardiovascular mortality.
- All-cause and cardiovascular hospitalization.
- Recurrence of myocarditis/pericarditis.
- Constrictive pericarditis.

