#### **4.5.2 Inclusion criteria for COVID-19 associated myocarditis/pericarditis**

1. COVID-19 infection within the previous 42 days.

AND

2. Myocarditis/pericarditis as per Brighton Criteria for vaccine associated myocarditis/pericarditis.

AND

3. No alternative cause of presentation.

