#### **4.5.3 Inclusion criteria for MIS-C/A myocarditis/pericarditis**

1. Brighton case definition for MIS-C/A (Level 1 to 3b).

AND

2. Myocarditis/pericarditis as per Brighton Criteria for vaccine associated myocarditis/pericarditis.

AND

3. No alternative cause of presentation.

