#### **4.8 Cohort time period**

The cohort entry start date is December 1, 2020. This date corresponds to the first authorization of mRNA vaccine in Canada by Health Canada (Pfizer BioNTech on December 9, 2020). The cohort entry end date will be determined by renewal of funding for the surveillance study by the Public Health Agency of Canada.

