**Level 1 of Diagnostic Certainty – Definitive Case**

OR

Personal history of confirmed COVID-19 within 12 weeks

OR

Close contact with known COVID-19 case within 12 weeks

OR

Following SARS-CoV-2 vaccinationg.**Level 2 of Diagnostic Certainty – Probable Case****Level 2a**

Same criteria as Level 1 except:

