**Footnotes:**

Note: At all levels of certainty, minimal to mild respiratory symptoms may be present and their presence does not exclude a case of MIS-C/A, however, a case must be excluded if there is concern for acute COVID-19-related pulmonary disease. Further, one of the critical components of the case definition is that it is only applied when there is no clear alternative diagnosis for the reported event.

a MIS-C = multisystem inflammatory syndrome in children, MIS-A = multisystem inflammatory syndrome in adults, CRP = C reactive protein (detected by any measure), ESR = erythrocyte sedimentation rate, BNP = brain natriuretic protein, NT-proBNP = N terminal pro-BNP, EKG = electrocardiogram, SARS-CoV-2 = severe acute respiratory syndrome coronavirus-2, COVID-19 = coronavirus disease 2019.

b Laboratory values are defined as low or high based on local laboratory normal ranges.

c Echocardiographic signs: dysfunction, wall motion abnormality, coronary abnormality (dilation, aneurysm, echobrightness, lack of distal tapering), valvular regurgitation, pericardial effusion, evidence of abnormal left ventricular strain.

d Physical stigmata of heart failure: gallop (IF diagnosed by expert) or rales, lower extremity edema, jugular venous distension, hepatosplenomegaly.

e EKG changes consistent with myocarditis or myo-pericarditis: abnormal ST segments and/or arrhythmia and/or pathologic Q waves and/or AV conduction delay and/or PR segment depression and/or low voltage QRS.

f Laboratory evidence of SARS-CoV-2 infection: serologic evidence of SARS-CoV-2 infection or SARS-CoV-2 nucleic acid amplification positivity or SARS-CoV-2 antigen positivity.

g If a known or suspected COVID-19 infection has not occurred within the preceding 12 weeks.

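### Primary MACE is counted only from vaccination, so never-vaccinated COVID-19 and MIS-C/A patients have no time zero, and those vaccinated more than 42 days before onset cannot score a myocarditis-related event

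*Protocol*

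**What the plan says.** Protocol 3.1 sets the MACE objective "in patients with vaccine associated myocarditis/pericarditis, COVID-19 myocarditis/pericarditis, and MIS-C/A myocarditis". Section 3.3 introduces a single list of primary endpoints for the three primary objectives. The one that answers the MACE objective is "Composite MACE at 30 days post vaccination (preferred by cardiovascular community) and at 42 days post vaccination". Section 3.4 puts the components on the same clock: "Individual components of primary composite endpoint at 30 days and 42 days post vaccination". Section 5 makes the vaccination date the baseline date for follow-up timing, with no exception by etiology.

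Entry to two of the three cohorts does not depend on vaccination:

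- **COVID-19 cohort (4.5.2):** the exposure is "COVID-19 infection within the previous 42 days".
- **MIS-C/A cohort (4.5.3 and Appendix 6):** levels 1 to 3b of the case definition qualify. At level 1 the link to SARS-CoV-2 may be laboratory-confirmed infection, "Personal history of confirmed COVID-19 within 12 weeks", or close contact with a case. Vaccination is a further alternative, with the condition in footnote g: "If a known or suspected COVID-19 infection has not occurred within the preceding 12 weeks".

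Diagnosis also appears as a time origin, in 4.10 and section 5, but only for the 3-month, 12-month and annual follow-up.

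**The concern.** An incidence at 30 or 42 days needs an origin that every patient has and that does not place the whole window before the disease starts. Vaccination meets this for the vaccine cohort, whose members were all vaccinated in the 42 days before they qualified. It fails for part of the other two cohorts.

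The two failures act differently. Patients with no vaccination date drop out of the 30- and 42-day figures. If patients with an old vaccination date are kept in the denominator, they cannot contribute a myocarditis-related event to the numerator. The reported MACE incidence for COVID-19 and MIS-C/A would then depend partly on when patients were last vaccinated, and would not be a clean measure of how severe their disease was. Setting those figures beside the vaccine cohort would mislead.

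**Working it through.** **1. Which cohorts have a day 0**

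| Cohort | Entry exposure | Vaccination required? | Origin of 30/42-day MACE |
|---|---|---|---|
| Vaccine associated (4.5.1) | vaccination within 42 days | yes | vaccination |
| COVID-19 (4.5.2) | infection within 42 days | no | vaccination |
| MIS-C/A (4.5.3, Appendix 6) | infection, COVID-19 history, close contact, or vaccination | no | vaccination |

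The protocol states no other origin for MACE.

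**2. Window left after onset**

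Let d be the days from vaccination to onset and W the window (30 or 42). Days left = max(0, W − d). I take d from the most recent dose, the reading kindest to the plan, because the protocol does not say which dose sets the date.

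| d | Left of 30 | Left of 42 |
|---|---|---|
| 0 | 30 | 42 |
| 14 | 16 | 28 |
| 30 | 0 | 12 |
| 42 | 0 | 0 |
| 60, 90, 180 | 0 | 0 |
| never vaccinated | undefined | undefined |

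For d above 42, both windows closed before onset. An unrelated earlier event could still fall inside them, but a myocarditis-related one cannot.

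**3. Possible dilution (assumed inputs)**

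Let p be the share of the denominator with closed windows, scored event-free and with the same true risk as the rest. Reported incidence is at most true × (1 − p). It is an upper limit because patients vaccinated shortly before onset also lose part of their window. With an assumed true risk of 20%:

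- p = 10%: 0.20 × 0.90 = 18%
- p = 25%: 0.20 × 0.75 = 15%
- p = 50%: 0.20 × 0.50 = 10%
- p = 75%: 0.20 × 0.25 = 5%

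**4. Would an infection clock repair it?**

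Not for MIS-C/A. Section 2.6 puts MIS-C onset at 2 to 6 weeks after infection. Onset on day 14 leaves 30 − 14 = 16 and 42 − 14 = 28 days. Onset on day 42 leaves 0 and 0. Appendix 6 admits cases up to 12 weeks, or 84 days.

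**5. Vaccine cohort (lesser point)**

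Entry runs to day 42, so a case arising on days 31 to 42 cannot contribute even its presenting MACE to the 30-day figure. The cohort of 20 patients cited in 2.10 had onset within 10 days, which leaves 20 to 30 of 30 days and 32 to 42 of 42. With onset assumed exponential and truncated at day 42:

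| Assumed mean onset before truncation (days) | Onset after day 30 | Mean days left of 30 | Mean days left of 42 |
|---|---|---|---|
| 4 | 0.05% | 26.0 | 38.0 |
| 7 | 1.1% | 23.2 | 35.1 |
| 14 | 7.1% | 18.6 | 30.2 |

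MACE present at presentation still counts if presentation falls inside the window, so lost days are not lost events in proportion.

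**The case against.** The strongest reply is that the post-vaccination wording was carried over from the vaccine cohort, and that the SAP announced in 6.3 can supply an index date for the others. Usable anchors exist: 2.4 names infection as the precipitant of COVID-19 myocarditis, and 4.10 times chart extraction from diagnosis for all three cohorts. But neither is linked to 30- or 42-day MACE. The vaccination clock stands in 3.3, 3.4 and section 5, so an SAP would have to replace a stated primary endpoint, a secondary endpoint and the baseline rule. That goes beyond analysis detail.

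Several narrower objections do stand:

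- The protocol does not say that closed-window patients will be scored as non-events. The dilution figures show one way of applying the text and do not estimate its effect in this study.
- The onset distribution in the vaccine cohort is assumed. Both windows there are deliberate choices with reasons given.
- Section 4.8 says "The cohort entry start date is December 1, 2020", eight days before the authorization on December 9 that it cites. This only illustrates that unvaccinated patients can enter; 4.5.2 and 4.5.3 settle it without that gap.
- Appendix 7 is an outline, so a date it does not list may still be collected.
- Objective 1 is descriptive and no sample-size figure depends on it. The treatment comparison and risk score for MACE are confined to vaccine-associated cases. Mortality and hospitalization in 3.4 carry no vaccination window, and some events could be re-timed from collected dates.

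These points limit the size of the damage. They do not give the primary endpoint an origin in the patients who lack one.

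**Conclusion.** The concern holds. For part of two of the three cohorts in primary objective 1, the MACE endpoint is either undefined (never vaccinated) or unable to register a myocarditis-related event (last dose more than 42 days before onset). This follows from the entry criteria and date arithmetic and needs no assumption.

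The size does need assumptions: the share of patients affected, their risk and how they are scored. Under those set out above, an assumed 20% risk would be reported as at most 18% to 5%. The day 31 to 42 issue in the vaccine cohort is secondary and may touch only a small minority. Because a primary endpoint cannot be applied as written to all the patients it is meant for, it must be corrected before analysis.

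**What to change.** 1. In 3.3 and 3.4, define a MACE time zero that exists in every cohort. Choose one date. Initial presentation is safer than formal diagnosis because events between the two then count. Treat deaths before diagnosis, or cases found at autopsy, as day-0 events.
2. Report 30- and 42-day MACE and its components from that date for all three cohorts.
3. Keep the 30- and 42-day post-vaccination windows for the vaccine cohort only, for comparison with vaccine surveillance. State which dose sets the date, which reading is primary, and that cases arising on days 31 to 42 contribute only to the 42-day figure.
4. Reconcile 3.3, 3.4, 4.10 and section 5 so that each endpoint and visit has one stated clock. Section 5 now times follow-up from diagnosis and also assigns vaccination as the baseline.
5. List the myocarditis/pericarditis presentation date explicitly in Appendix 7, where a diagnosis date is named only under COVID-19 infection.

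The cost is protocol wording, one explicit date field and one additional table. Sections 4.10 and 5 already presuppose a diagnosis or presentation date. The common-clock figure will not compare directly with reports that count days after vaccination, which is the reason for step 3. No sample-size figure changes.

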## 4.5 Inclusion criteria

### 4.5.1 Inclusion criteria for vaccine associated myocarditis/pericarditis.

1. COVID-19 vaccination within previous 42 days.

AND

2. At least one cardiac symptom of suspected myocarditis/pericarditis (Appendix 5).

OR

At least two non-specific symptoms (Appendix 5).

OR

In infants and young children, at least two non-specific pediatric symptoms (Appendix 5).

OR

No symptoms, but abnormal histopathology or a combination of abnormal cardiac biomarkers with abnormal cardiac imaging (echo or MRI).

AND

3. At least one of the following objective findings (Brighton Criteria case definitions, Appendices 1 to 5):
  - a. Histopathologic examination of myocardial tissue (autopsy or endomyocardial biopsy) showed myocardial inflammation.
  - b. Elevated myocardial biomarker (Troponin T, Troponin I, or CK-MB).
  - c. Cardiac MRI abnormality.
  - d. Echocardiographic abnormality.
  - e. New or worsening arrhythmia on electrocardiogram, Holter monitor, or telemetry.
  - f. Elevated inflammation biomarkers: ESR, CRP, hs-CRP, or D-Dimer.
  - g. Physical examination pericardial friction rub or pulsus paradoxus.
  - h. Pericardial fluid or inflammation by imaging (echo, MRI, or CT).
  - i. Enlarged heart on chest radiograph.

AND

4. No alternative cause of presentation. e.g. infectious or autoimmune myocarditis.

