### **5. VISIT SCHEDULE AND PROCEDURES**

Consenting patients will be followed up clinically by their regular physician (e.g. Cardiologist, Internist, other physician) in collaboration with their local site-PIs, in accordance with the 2022 ACC/AHA standard of care guidelines for the management of myocarditis.

Patients will be followed at 3 months and 12 months after diagnosis and annually thereafter for up to 3 years. To standardize follow-up timing the date of vaccination will be assigned as the baseline date. However, baseline visit data will be collected from initial presentation and medical contact which is usually the date of diagnosis. This distinction is made because there is a variation between cases in date of vaccination to date of diagnosis/initial presentation.

The case report form variable list (Appendix 7) outlines the essential elements to be collected including demographic data, vaccination status, presenting symptoms, physical examination findings, diagnostic testing (routine laboratory work, electrocardiogram, MRI), treatments, and patient outcomes. Quality of life, depression, anxiety, and physical activity will be measured at baseline, 3 months, 12 months, and annually thereafter using validated instruments: quality of life EQ-5D-5L questionnaire for adults or EQ-5D-Y questionnaire for children; depression PHQ-9 and anxiety GAD-7; physical activity International Activity Questionnaire. These will be conducted at clinical visits or by telephone if no concurrent clinical visit is scheduled.

Baseline data will be collected for all etiologies of myocarditis, but thereafter follow-up visits will only be undertaken for patients with vaccine associated myocarditis/pericarditis, COVID-19 myocarditis/pericarditis, and MIS-C/A myocarditis/pericarditis (i.e. not alternative etiology myocarditis).

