## 7. APPENDICES

## 7.1 Appendix 1. Brighton Collaboration myocarditis case definition and levels of diagnostic certainty

Level of certainty 1 (definitive case)	
Histopathologic examination of myocardial tissue (autopsy or endomyocardial biopsy) showed myocardial inflammation	
OR	
Elevated myocardial biomarkers (at least one of the findings below)	
	Troponin T
	Troponin I
AND	
Abnormal imaging study	
	Abnormal cardiac magnetic resonance study (at least one of the findings below)
	Edema on T2-weighted study, typically patchy in nature
	Late gadolinium enhancement on T1-weighted study with an increased enhancement ratio between myocardial and skeletal muscle typically involving at least one non-ischemic regional distribution with recovery (myocyte injury).
OR	
	Abnormal echocardiogram (at least one of the findings below)
	New focal or diffuse left or right ventricular function abnormalities (e.g., decreased ejection fraction)
	Segmental wall motion abnormalities
	Global systolic or diastolic function depression or abnormality
	Ventricular dilation
	Wall thickness change
Level of certainty 2 (probable case)	
Clinical symptoms	
	Cardiac symptoms (at least one finding below)
	Acute chest pain or pressure
	Palpitations
	Dyspnea after exercise, at rest, or lying down
	Diaphoresis
	Sudden death
OR	
	Non-specific symptoms (at least two findings below)
	Fatigue
	Abdominal pain
	Dizziness or syncope
	Edema
	Cough
OR	
	Infants and young children (at least two findings below)
	Irritability
	Vomiting
	Poor feeding
	Tachypnea
	Lethargy
AND	
Testing supporting diagnosis (biomarkers, echocardiogram, and electrocardiogram)	
	Abnormal cardiac magnetic resonance study (see level 1 case definition)
OR	
	Elevated myocardial biomarkers (at least one of the findings below)
	Troponin T
	Troponin I
	Creatine kinase-myocardial band
OR	
	Abnormal echocardiogram (See level 1 case definition)
OR	
	Electrocardiogram abnormalities that are new and/or normalize on recovery (at least 1 of the findings below)
	Paroxysmal or sustained atrial or ventricular arrhythmias (premature atrial or ventricular beats, and/or supraventricular or ventricular tachycardia, interventricular conduction delay, abnormal Q waves, low voltages)
	AV nodal conduction delays or intraventricular conduction defects (atrioventricular block (grade I-III), new bundle branch block)
	Continuous ambulatory electrocardiographic monitoring that detects frequent atrial or ventricular ectopy
AND	

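### The only MACE definition runs from vaccination and does not exclude findings at presentation, so it does not suit the treatment comparison or the risk score, and it gives no sure time origin outside the vaccine cohort

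*Protocol*

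**What the plan says.** Section 3.3 sets the first primary endpoint as "Composite MACE at 30 days post vaccination (preferred by cardiovascular community) and at 42 days post vaccination (preferred by vaccine monitoring investigators"). It lists six components: death, ventricular arrhythmia, heart block, heart failure, "Left ventricular systolic dysfunction (left ventricular ejection fraction [LVEF] <55" per cent), and tamponade. None has to be new after presentation. Section 3.4 keeps the same windows: "Individual components of primary composite endpoint at 30 days and 42 days post vaccination".

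Entry to the vaccine-associated cohort requires "COVID-19 vaccination within previous 42 days" (section 4.5.1). Section 5 adds "To standardize follow-up timing the date of vaccination will be assigned as the baseline date", while "baseline visit data will be collected from initial presentation and medical contact which is usually the date of diagnosis". Presentation therefore falls after the time origin, and for cases diagnosed by day 30 it falls inside both windows.

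The case definition in Appendix 1 includes "Paroxysmal or sustained atrial or ventricular arrhythmias (premature atrial or ventricular beats, and/or supraventricular or ventricular tachycardia"), "AV nodal conduction delays or intraventricular conduction defects (atrioventricular block (grade I-III), new bundle branch block"), decreased ejection fraction on echocardiography, and sudden death as a cardiac symptom.

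Among the secondary objectives (section 3.2), one compares MACE between treated and untreated vaccine-associated cases and another builds a risk score for MACE. Neither names a window or a time origin. Primary objective 1 (section 3.1) applies MACE to COVID-19 and MIS-C/A cases as well.

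**The concern.** A treatment comparison needs outcomes that follow the treatment decision, and a prediction score needs outcomes that follow measurement of the predictors. A MACE counted from vaccination guarantees neither. A low LVEF on the first echocardiogram may influence whether a drug is given and also count as that drug's outcome. Section 2.8 makes such a link plausible: it reports guidance that anti-inflammatory drugs may not be needed when, among other conditions, LVEF is normal. In a risk score, the same echocardiogram or ECG could sit on both sides of the model.

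The origin also makes follow-up after diagnosis depend on how late the patient was diagnosed. And for cohorts defined by infection rather than vaccination, the endpoint may have no starting date.

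At stake are two secondary objectives, one of them on a treatment question that section 2.8 says lacks evidence, and the meaning of the primary MACE rate in two of the three cohorts.

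**Working it through.** **The plan's own figures.** The protocol attaches no MACE rate, power or effect size to this endpoint. Its lower sample limit (section 6.2) reproduces: 0.60 × 810 = 486. That figure and the 1,061 reported cases are used below.

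**Overlap of outcome and case definition.** Section 3.3 against Appendix 1: death and sudden death; ventricular tachycardia in both; second- or third-degree block within AV block of grades I to III; LVEF under 55% and decreased ejection fraction. That is four of six components. Section 3.3 also uses LVEF under 55% as a baseline state, for the second primary endpoint.

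**Days after diagnosis inside each window** (from the protocol alone). For diagnosis on day t: max(0, 30 − t) and max(0, 42 − t).

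| Day of diagnosis | 30-day endpoint | 42-day endpoint |
|---|---|---|
| 3 | 27 | 39 |
| 21 | 9 | 21 |
| 35 | 0 | 7 |

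Cases diagnosed on days 31 to 42 stay in the 30-day denominator but cannot contribute an event at or after diagnosis.

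**Treatment comparison with no drug effect** (all rates assumed). Let p be the share presenting with low LVEF, tL and tN the shares treated among those with and without it, and e the later event rate in the rest.

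- Treated risk = [p·tL + (1−p)·tN·e] / [p·tL + (1−p)·tN]. Untreated: replace tL and tN by 1−tL and 1−tN.
- Centre case, p = 0.20, tL = 0.80, tN = 0.60, e = 0.03: treated (0.16 + 0.0144)/0.64 = 27.3%; untreated (0.04 + 0.0096)/0.36 = 13.8%; RR 1.98.
- Range over p 0.10–0.30 and e 0.01–0.10, with tN = 0.60: RR 0.72–0.84 if tL = 0.50; exactly 1.00 if tL = 0.60; 1.20–1.43 if 0.70; 1.47–2.22 if 0.80.
- Deaths before treatment push the other way. With d = 0.25%, 0.5% or 1% dying untreated, 60% of the others treated, and 3% events in both groups, untreated risk = [d + (1−d)·0.4·0.03]/[d + (1−d)·0.4] = 3.60%, 4.20%, 5.39%. RR = 0.83, 0.71, 0.56.

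**Does redefinition alone cure it?** Count only later events, at an assumed 10% in those presenting with low LVEF and 3% in the rest. The centre case gives treated (0.016 + 0.0144)/0.64 = 4.75%; untreated (0.004 + 0.0096)/0.36 = 3.78%; crude RR 1.26. With tL = 0.50 it is 0.90. It is 1.00 within strata of presenting LVEF by construction, so adjustment is needed as well.

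**Risk score.** With presenting MACE findings in 5–20% and unrelated later events in 2–5%, a flag for the presenting finding alone reaches an AUC of 0.76–0.96 for the combined endpoint (simulation). Its AUC for later events is 0.50 by construction.

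**How much the window matters.** At an assumed 3% per 30 days after diagnosis, captured risk is 1 − 0.97^(days/30). The 30-day endpoint captures 2.7% for diagnosis on day 3, 0.9% on day 21 and 0% on day 35. If 20% present with low LVEF and only the rest are at later risk, the combined 42-day figure is 0.20 + 0.80 × captured risk = 23.1%, 21.7% and 20.6% for days 3, 21 and 35. The distortion is large mainly at 30 days.

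**The case against.** The strongest reply is that section 3.3 defines endpoints for the primary objectives only. The two affected objectives are secondary, and section 6.3 assigns the analysis to a separate plan. That plan could set an outcome counted from diagnosis without contradicting section 3.3, since section 4.10 follows charts for up to three years from diagnosis. This stands in part. Landmark timing and severity adjustment belong in the analysis plan. But the protocol offers only one MACE with one origin, and its objectives use that term unqualified.

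Second, no sentence says that presenting findings count. True: this is a reading of the definition. Appendix 8 leaves its outcomes row blank at baseline, but that row starts at 3 months, after both windows have closed, and the same table records events at baseline. The text is silent, not exclusionary.

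Third, vaccination as origin is a deliberate choice, and section 5 acknowledges the variable interval to diagnosis. That supports a descriptive rate, but not the other two uses.

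Fourth, the illustrated bias needs treatment to be related to presenting findings, and part of it survives redefinition. Both are correct. A reader might infer that the comparison will make drugs look harmful, or protective. The documents support neither, because they give no rates and plausible mechanisms pull in both directions.

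**Conclusion.** The concern holds as a stated definition that fits two of its apparent uses badly. The overlap of components and the day counts come from the protocol itself. Two links are natural readings, not explicit statements: that presenting findings count, and that section 3.2 uses this MACE. Every risk ratio, AUC and event rate above is assumed. The range of 0.72 to 2.22 shows that the distortion could matter; it does not show that it will occur or which way it would go.

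It would go too far to call the primary MACE rate invalid. For vaccine-associated cases it is acceptable as description, and the 42-day figure is the cleaner one. It would also go too far to clear it everywhere: COVID-19 and MIS-C/A cases (sections 4.5.2 and 4.5.3) can enter with no recent vaccination, so the windows may have no start. The weight is minor to moderate, and the change should be made before analysis.

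**What to change.** 1. Keep the 30/42-day rate as description for vaccine-associated cases, labelled *MACE at or after presentation*. Note that the 30-day figure cannot include events at or after diagnosis in cases diagnosed on days 31 to 42. State a time origin, such as diagnosis, for the COVID-19 and MIS-C/A cohorts.
2. Report MACE features at presentation separately from incident MACE.
3. For the two secondary objectives, define incident MACE as new events over a fixed window that starts at diagnosis (risk score) or at a treatment-decision landmark (treatment comparison). Leave landmark timing and severity adjustment to the analysis plan, and say that redefinition alone does not remove confounding by indication.
4. Keep patients with presenting LVEF under 55% at risk for the other components. Report LVEF dysfunction after baseline separately, with a stated rule for worsening from an already low value. Repeat imaging is planned only after an abnormal first test (section 5.1.2, Appendix 8), so detection is selective.

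**Cost.** Endpoint wording, plus a check that the case report form dates echocardiography, MRI, events and start of treatment. Appendix 7 is an outline and does not show that these dates are uncollected, though some will be missing from retrospective charts.

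There will be fewer events. At 486 cases the centre case gives 486 × 0.224 ≈ 109 combined events, but 97.2 × 0.10 + 388.8 × 0.03 ≈ 21 incident ones (21/486 = 4.3%, 95% CI 2.8–6.5%). At 1,061 cases the figures are about 238 and 47. With later rates of 1–10% in the rest and 3–20% in those presenting with low LVEF, incident events run from 7 to 58 at 486 cases and from 15 to 127 at 1,061. Whether that supports a multivariable score cannot be judged from the protocol.

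### Vaccine cases can arise up to day 42 but one primary MACE time point is day 30 post vaccination, so cases arising on days 31 to 42 lower the 30-day rate if they stay in its denominator

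*Protocol*

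**What the plan says.** Four parts of the protocol bear on this point.

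- **Endpoint.** Section 3.3 defines the first primary endpoint as "Composite MACE at 30 days post vaccination (preferred by cardiovascular community) and at 42 days post vaccination". Section 3.4 repeats both time points for the components: "Individual components of primary composite endpoint at 30 days and 42 days post vaccination".
- **Entry.** Section 4.5.1 requires "COVID-19 vaccination within previous 42 days" for the vaccine cohort. It does not say whether the 42 days run to symptom onset, presentation or diagnosis.
- **Clock.** Section 5 states: "To standardize follow-up timing the date of vaccination will be assigned as the baseline date". It explains that "there is a variation between cases in date of vaccination to date of diagnosis/initial presentation".
- **Denominator.** No section limits the 30-day endpoint to cases already ill by day 30, and none restarts the MACE clock at onset or diagnosis.

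**The concern.** The entry window is 12 days longer than the first endpoint window, and both start at vaccination. Take a patient whose myocarditis begins on day 35. The patient meets the vaccine criterion and belongs to the cohort, but at day 30 did not yet have the disease. Even if the patient arrives in ventricular fibrillation on day 35, the 30-day endpoint records no event.

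Such patients are structural zeros in a primary endpoint. For death the zero is exact, because a patient must be alive on day 30 to become a case on day 35. For the other components, nothing caused by the episode can occur before it starts. The objective in section 3.1 is the incidence of events in patients who have the condition, so a denominator that includes people who do not yet have it answers a different question, and answers it too low.

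**Working it through.** **Inputs.** The endpoint days (30 and 42) come from section 3.3, the entry limit (42 days) from section 4.5.1, and the vaccination origin from section 5. The protocol gives no MACE rate and no distribution of onset times, so it has no figure of its own to reproduce here. The case number used for scale, 486, is the lower limit in section 6.2.

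**Step 1: illness time before each time point.** For onset on day t, this is max(0, 30 − t) and max(0, 42 − t).

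| Onset day | Days ill by day 30 | Days ill by day 42 |
|---|---|---|
| 3 | 27 | 39 |
| 10 | 20 | 32 |
| 20 | 10 | 22 |
| 30 | 0 | 12 |
| 31 | 0 | 11 |
| 36 | 0 | 6 |
| 42 | 0 | 0 |

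Every onset from day 31 on has no illness time by day 30. The table also shows that illness time differs widely among earlier onsets, and that a day-42 onset has none at day 42 either.

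**Step 2: effect on the rate.** Let p be the 30-day rate among cases with onset by day 30, and f the share of cases arising on days 31 to 42. If all cases stay in the denominator:

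observed 30-day rate = p × (1 − f) + 0 × f = p(1 − f).

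**Step 3: illustration.** Both p = 20% and the values of f are assumptions. The number of late cases is 486 × f.

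| f | 30-day rate | Loss (points) | Late cases of 486 |
|---|---|---|---|
| 2% | 19.6% | 0.4 | about 10 |
| 5% | 19.0% | 1.0 | about 24 |
| 10% | 18.0% | 2.0 | about 49 |
| 20% | 16.0% | 4.0 | about 97 |

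**Step 4: scale.** The standard error of a 20% rate with 486 cases is √(0.20 × 0.80 / 486) = 0.018, or 1.8 points. At f = 2% the loss is well inside it. At f = 10% the loss slightly exceeds it. More cases shrink the standard error but not the loss.

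**The case against.** **The denominator may be settled elsewhere.** Section 6.3 promises a statistical analysis plan, which is not among the documents, and such a plan could drop late cases from the 30-day analysis. That stands, and is why the conclusion is conditional on their being kept. But the entry window, the endpoint days and the origin are all fixed in the protocol, and followed as written they produce the dilution.

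**The quantity is coherent.** The share of confirmed cases with MACE by day 30 after vaccination is a definable surveillance figure, and section 5 chose the vaccination origin on purpose. It is low only when read as the risk in people who have the disease. Section 3.1 invites that reading, so this objection stands only in part.

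**Day 42 covers the whole entry window.** True: events on days 31 to 42 still count in a primary endpoint. That does not repair the 30-day endpoint, which is also primary.

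**Stronger readings that a reader might infer.**

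- *A material bias.* The documents do not support this. They give neither f nor a MACE rate, and if onsets are mostly early the loss is trivial.
- *A rise from day 30 to day 42 will be misread as late MACE.* If every MACE occurred at presentation, at a 20% rate, the 42-day rate would be 20%, and f of 2% to 20% would produce an apparent rise of 0.4 to 4.0 points with no patient worsening. But that assumption maximises the artefact, and no section plans to compare the two rates. The protocol offers them as the preferences of two audiences.
- *The risk score and the treatment comparison in section 3.2 are distorted.* The protocol does not say which time point they use.

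**Conclusion.** The mismatch is real. On the protocol's text, an eligible vaccine case first arising on days 31 to 42 cannot contribute a 30-day event from its episode, and keeping it in the denominator multiplies the 30-day rate by (1 − f). The same holds for each component in section 3.4.

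The direction is certain and the size is not. With an assumed 20% rate and f between 2% and 20%, the 30-day rate would read 19.6% to 16.0%. The result rests on three conditions:

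- Late cases remain in the denominator.
- Day of entry reflects onset. A patient presenting on day 35 may have fallen ill before day 30, which would make f smaller.
- Non-fatal components are counted only when they arise from the episode. An unrelated abnormality, such as a low ejection fraction that was present before the episode, could break the zero.

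This is a cheap correction to a primary endpoint definition. It is not evidence that the study's main result will be misleading.

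**What to change.** In sections 3.3 and 3.4:

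1. Restrict the denominator of the 30-day post-vaccination MACE endpoint and its components to vaccine cases whose episode began by day 30. Use the date of symptom onset where it is recorded, and otherwise the date of first presentation or diagnosis.
2. Keep the full vaccine cohort for the 42-day endpoint, and also report the 42-day rate in the by-day-30 subset, so that the two rates rest on the same patients.
3. State that neither time point gives equal follow-up after onset. The restriction removes the structural zeros but leaves a day-30 onset with no illness time at day 30, and a day-42 onset with none at day 42.

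The fallback date is needed for two reasons. Appendix 7 lists a symptom-onset date only under COVID-19 infection and none for the cardiac episode. Section 4.5.1 also admits patients without symptoms, who have no onset date.

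The cost is a sentence or two in each section, a slightly smaller 30-day denominator, and some onset dates approximated by presentation or diagnosis, which will place a few cases on the wrong side of day 30. Vaccination dates are already collected under Appendix 7. The date of diagnosis is needed anyway, because section 5 schedules follow-up from it: "Patients will be followed at 3 months and 12 months after diagnosis and annually thereafter for up to 3 years".
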